5.4.3 Other Efficacy Analyses

CCI

5.5 Pharmacokinetic, Pharmacodynamic, and PHARMACOGENOMIC/PHARMACOGENETIC ANALYSES

Perampanel plasma concentrations were obtained from blood samples drawn at Weeks 7, 13 and 19/ET visit. A listing of perampanel plasma concentrations will be produced. Details of the analysis methods for population pharmacokinetic/pharmacodynamics (PK/PD) modeling will not be described in this statistical analysis plan (SAP) but will be described in a separate analysis plan.

Pharmacogenomics analyses may be performed and will be reported separately. Details of these analyses will be described in a separate analysis plan if appropriate.

5.6 SAFETY ANALYSES

All safety analyses will be performed on the Safety Analysis Set. Safety data, presented by treatment group, will be summarized on an “as treated” basis using descriptive statistics (e.g., n, mean, standard deviation, median, minimum, maximum for continuous variables; n [%] for categorical variables). Safety variables include treatment-emergent adverse events (TEAEs), clinical laboratory parameters, vital signs, Study Day 1 for all safety analyses is defined as the date of the first dose of study drug.

Summaries of exposure, TEAEs and treatment-emergent markedly abnormal values (TEMAVs) will be presented by age group.

5.6.1 Extent of Exposure

Duration of Randomization Phase (Titration Period + Maintenance Period) exposure will be calculated as the number of days between the date the subject received the first dose of study drug and the date the subject received the last dose of study drug in the Randomization Phase. The results will be summarized by treatment groups using median, mean, standard deviation, minimum, maximum, and number of subjects with non- missing data.

Exposure to the study medication will also be summarized by categories of cumulative weeks.

The mean, modal, median, maximum and last daily dose over the Titration and Maintenance Periods for each of the randomized treatment arms will be summarized. The mean daily dose for each of the arm will be calculated by taking the average of all the doses taken weighted by the total duration of exposure and rounded to 1 decimal place, ie sum of (days on each dose*dose)/total dose duration of subjects. For subjects ≥ 12 years, dose will be summarized in mg. For subjects < 12 dose will be summarised in mg/kg.

The number of subjects who down-titrated or discontinued at their maximum daily dose will be summarized.

Cumulative extent of exposure and summaries of dose will be presented by age group.

5.6.2 Adverse Events

The AE verbatim descriptions (investigator terms from the CRF) will be classified into standardized medical terminology using the Medical Dictionary for Regulatory Activities (MedDRA). Adverse events will be coded to the MedDRA (Version 24.1 or higher) lower level term (LLT) closest to the verbatim term. The linked MedDRA preferred term (PT) and primary system organ class (SOC) will also be captured in the database.

A TEAE is defined as an AE that emerged during treatment, having been absent at pre-treatment (Baseline) or

- Re-emerged during treatment, having been present at pre-treatment (Baseline) but stopped before treatment, or
- Worsened in severity during treatment relative to the pre-treatment state, when the AE was continuous.

Only those AEs that are treatment emergent will be included in summary tables. All AEs, treatment emergent or otherwise, will be presented in subject data listings.

TEAEs will be summarized by treatment group and by age group. The incidence of TEAEs will be reported as the number (percentage) of subjects with TEAEs by SOC and PT. A subject will be counted only once within a SOC and PT, even if the subject experienced more than one TEAE within a specific SOC and PT. The number (percentage) of subjects with TEAEs will also be summarized by maximum severity (mild, moderate, or severe).

The number (percentage) of subjects with TEAEs will also be summarized by relationship to study drug (related and not related). Summaries of treatment-related TEAEs will be produced.

There will also be summaries of TEAEs by dose at onset and exposure-adjusted event rates.

5.6.2.1 Deaths, Other Serious Adverse Events, and Other Significant Adverse Events

A subject data listing of all AEs leading to death will be provided.

The number (percentage) of subjects with treatment-emergent serious adverse events (SAEs) will be summarized by MedDRA SOC and PT for each treatment group, ~~overall and by pooled country~~. A subject data listing of all SAEs will be provided.

The number (percentage) of subjects with TEAEs leading to discontinuation from study drug will be summarized by MedDRA SOC and PT for each treatment group. A subject data listing of all AEs leading to discontinuation from study drug will be provided.

The number (percentage) of subjects with TEAEs leading to dose adjustment will be summarized by MedDRA SOC and PT for each treatment group. A subject data listing of all AEs leading to dose adjustment will be provided.

5.6.2.2 Adverse Events of Special Interest

A listing and summary of subjects with AEs related to suicidality, identified by the depression and suicide/self-injury standardized MedDRA query (SMQ) terms, will be provided. TEAEs of special interest listed below will be summarized by SOC and PT for each treatment group.

SMQs will be used to identify relevant terms for the following TEAEs. All of these TEAEs will be summarized by broad and narrow terms, except those related to abuse potential, hostility/aggression and psychosis/psychotic disorder, which will be summarized by both broad and narrow terms and by narrow terms.

- TEAEs suggestive of abuse potential: SMQ of drug abuse, dependence and withdrawal
- TEAEs related to alertness and cognition: SMQ of dementia
- TEAEs related to hostility/aggression: SMQ of hostility/aggression
- TEAEs related to psychosis and psychotic disorder: SMQ of psychosis and psychotic disorders
- TEAEs related to status epilepticus/convulsions: SMQ of convulsions
- TEAEs related to drug related hepatic disorder abnormalities: SMQ of drug-related hepatic disorders
- Cardiac and electrocardiogram (ECG) TEAEs: SMQs of cardiac arrhythmia terms (incl bradyarrhythmias and tachyarrhythmias, arrhythmia related investigations, signs and symptoms, cardiac failure, cardiomyopathy, ischaemic heart diseases, and Torsade de pointes/QT prolongation
- Rash: SMQ of severe cutaneous adverse reactions and hypersensitivity

Falls will be summarized for Prerandomization Phase and Follow-up Period, and by actual dose of onset for the Titration Period and Maintenance Period.

Exposure-adjusted rates of falls and AEs in the accident/injury SMQ will be presented.

5.6.3 Laboratory Values

Laboratory results will be summarized using Système International (SI) units, as appropriate. Actual value and change from baseline in all quantitative parameters will be summarized by visit and treatment group for each postbaseline visit and to the end of treatment (defined as the last on-treatment value). Qualitative parameters will be summarized using frequencies at each visit. Whenever normal ranges are available, it will be determined whether the lab value is above (H), below (L) or within (N) the normal range.

Within-treatment comparisons for each laboratory parameter will be based on 3-by-3 tables (shift tables) that compare the baseline LNH classification to the LNH classification at each postbaseline

visit and at the end of treatment. Similar shift tables will be used to compare the baseline LNH classification to the LNH classification for the highest and lowest value during the treatment period.

The number of abnormal records and the number of subjects with two consecutive abnormal records will also be summarized.

The incidence of TEMAVs will be summarized over all scheduled and unscheduled visits for the parameters with defined notable ranges given in Section 13.1 of this analysis plan. A phosphate value will be determined to be a TEMAV if the post baseline National Cancer Institute (NCI) common toxicity criteria grade increases from baseline and the post baseline grade is greater than or equal to 3. For all other parameters in Section 13.1, a value will be determined to be a TEMAV if the post baseline NCI grade increases from baseline and the post baseline grade is greater than or equal to 2. The number (percentage) of subjects with TEMAVs will be displayed. Additionally the number of subjects with TEMAVs who were normal at baseline and the number of TEMAVs will also be summarized.

For alanine amino transferase (ALT), aspartate amino transferase (AST) and alkaline phosphatase, the number of subjects with $> 3x$ but $\leq 5x$ the Upper Limit Normal (ULN) and the number of subjects with $> 5x$ the ULN will be summarized by treatment group by visit. For bilirubin, the number of subjects with serum concentrations $> 2x$ ULN will be summarized by treatment group by visit. These summaries will also be provided for the maximum value in the treatment duration. In addition, the number of subjects who meet the criteria for Hy's Law at the same visit will be summarized by visit and during the treatment duration. A subject will be determined to have met Hy's Law if AST or ALT is $> 3x$ ULN, bilirubin $> 2x$ ULN, and alkaline phosphatase $\leq 2x$ ULN at a visit. The number of subjects who meet each of the criteria for Hy's Law during treatment (but not all necessarily at the same visit) will also be summarized.

Potentially clinically significant (abnormal) changes, defined as an increase in NCI grade to Grade 2 or higher from baseline when the baseline value is normal will be summarized.

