- Hospitalization for administration of study drug or insertion of access for administration of study drug
- Hospitalization for routine maintenance of a device (eg, battery replacement) that was in place before study entry

If possible, a blood sample for the measurement of study drug blood concentration should be drawn at the first report of an SAE or a severe unexpected AE and at its resolution.

LABORATORY MEASUREMENTS

Clinical laboratory tests to be performed, including hematology, chemistry, and urinalysis, are summarized in [Table 2](#). Subjects should be in a seated or supine position during blood collection.

The Schedule of Procedures/Assessments ([Table 5](#)) shows the visits and timepoints at which blood for clinical laboratory tests and urine for urinalysis will be collected in the study (Core Study).

Table 2 Clinical Laboratory Tests

| Category | Parameters |
|---------------------------|--|
| Hematology | hematocrit, hemoglobin, platelets, RBC count, and WBC count with differential (bands, basophils, eosinophils, lymphocytes, monocytes, neutrophils) |
| Chemistry | |
| Electrolytes | bicarbonate, chloride, potassium, sodium |
| Liver function tests | alanine aminotransferase, alkaline phosphatase, aspartate aminotransferase, direct bilirubin, total bilirubin |
| Renal function parameters | blood urea/blood urea nitrogen, creatinine |
| Other | albumin, calcium, cholesterol, globulin, glucose ^a , lactate dehydrogenase, phosphorus, total protein, lipid panel ^a , uric acid |
| Urinalysis | bacteria, casts, crystals, epithelial cells, glucose, ketones, occult blood, pH, protein, RBCs, specific gravity, WBCs |
| Viral tests | HbsAg, HepC |

HbsAg = Hepatitis B surface antigen; HepC = Hepatitis C; RBC = red blood cell, WBC = white blood cell.

a: Fasting samples to be taken at Baseline and at Visit 7 (end of Maintenance Period) or Early Discontinuation

Clinical laboratory tests during the study will be performed by a designated laboratory. All blood and urine samples will be collected and sent to the central laboratory on the day of collection unless otherwise instructed. In cases of a safety concern, blood samples will be split (or two samples drawn) to allow a local laboratory analysis in addition to the central laboratory. Laboratory certification as available may be included in the final clinical study report for this study.

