- e: Only for those subjects not rolling over into Extension A, and for those subjects who prematurely discontinued from the study, the Follow-up visits will take place at 1 week and 4 weeks after the last study drug administration (ie, Visit 7 or Early Discontinuation Visit, respectively). These visits will not be conducted if the subject continues into Extension A, in which case, a Follow-up visit will be performed 4 weeks after the last Extension visit. Visits will have a window of ± 6 days. (revised per Amendments 01 and 04)
- f: Final determination of eligibility and, if eligible, randomization to occur before any study drug administration. (revised per Amendment 04)
- g: Lifetime AED history will be collected as part of medical history.
- h: Height of adult subjects is to be recorded only at the Screening Visit (Visit 1). (revised per Amendment 01)
- i: CCI [REDACTED]
- j: [REDACTED]
- k: Subjects ≥ 8 years of age at time of informed consent/assent and subjects who will reach the age of 8 years during the double-blind phase of the study will also be assessed using the C-SSRS starting at Baseline. (revised per Amendment 03)
- l: Urine and serum pregnancy testing is for postpuberty, premenopausal females and postmenopausal females who have been amenorrheic for less than 12 months.
- m: Clinical laboratory tests include chemistry, hematology, and urinalysis. If a urine sample cannot be obtained; the subject will still be eligible for enrollment. However, every effort should be made to collect a sample.
- n: Fasting samples to be taken at indicated time points for glucose and lipid panel.
- o: Drug screen includes cocaine, phencyclidine [(PCP)], opioids ([as a group]), benzodiazepines, barbiturates, and amphetamines. Positive CBD results in subjects taking CBD products will not be exclusionary. (revised per Amendment 04)
- p: Collect diaries at Visit 7 from subjects not rolling over into Extension A. Dispense diaries at Visit 7 to subjects rolling over into Extension A.
- q: CCI [REDACTED]

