| Cholesterol, serum-high (hypercholesterolemia) | > ULN – 300 mg/dL > ULN – 7.75 mmol/L | > 300 – 400 mg/dL > 7.75 – 10.34 mmol/L | > 400 – 500 mg/dL > 10.34 – 12.92 mmol/L | > 500 mg/dL > 12.92 mmol/L |
| Creatinine | > ULN – 1.5 x ULN | > 1.5 – 3.0 x ULN | > 3.0 – 6.0 x ULN | > 6.0 x ULN |
| GGT (γ-Glutamyl transpeptidase) | > ULN – 3.0 x ULN | > 3.0 – 5.0 x ULN | > 5.0 – 20.0 x ULN | > 20.0 x ULN |
| Glucose, serum-high (hyperglycemia) | Fasting glucose value: > ULN – 160 mg/dL > ULN – 8.9 mmol/L | Fasting glucose value: > 160 – 250 mg/dL > 8.9 – 13.9 mmol/L | > 250 – 500 mg/dL; > 13.9 – 27.8 mmol/L; hospitalization indicated | > 500 mg/dL; > 27.8 mmol/L; life-threatening consequences |
| Glucose, serum-low (hypoglycemia) | < LLN – 55 mg/dL < LLN – 3.0 mmol/L | < 55 – 40 mg/dL < 3.0 – 2.2 mmol/L | < 40 – 30 mg/dL < 2.2 – 1.7 mmol/L | < 30 mg/dL < 1.7 mmol/L life-threatening consequences; seizures |
| Phosphate, serum-low (hypophosphatemia) | < LLN – 2.5 mg/dL < LLN – 0.8 mmol/L | < 2.5 – 2.0 mg/dL < 0.8 – 0.6 mmol/L | < 2.0 – 1.0 mg/dL < 0.6 – 0.3 mmol/L | < 1.0 mg/dL < 0.3 mmol/L life-threatening consequences |
| Potassium, serum-high (hyperkalemia) | > ULN – 5.5 mmol/L | > 5.5 – 6.0 mmol/L | > 6.0 – 7.0 mmol/L hospitalization indicated | > 7.0 mmol/L life-threatening consequences |
| Potassium, serum-low (hypokalemia) | < LLN – 3.0 mmol/L | < LLN – 3.0 mmol/L; symptomatic; intervention indicated | < 3.0 – 2.5 mmol/L hospitalization indicated | < 2.5 mmol/L life-threatening consequences |

| Sponsor's Grading for Laboratory Values | | | | |
|--|--|--|---|---|
| | Grade 1 | Grade 2 | Grade 3 | Grade 4 |
| Sodium, serum-high (hypernatremia) | > ULN – 150 mmol/L | > 150 – 155 mmol/L | > 155 – 160 mmol/L hospitalization indicated | > 160 mmol/L life-threatening consequences |
| Sodium, serum-low (hyponatremia) | < LLN – 130 mmol/L | N/A | < 130 – 120 mmol/L | < 120 mmol/L life-threatening consequences |
| Triglyceride, serum-high (hypertriglyceridemia) | 150 – 300 mg/dL 1.71 – 3.42 mmol/L | > 300 – 500 mg/dL > 3.42 – 5.7 mmol/L | > 500 – 1000 mg/dL >5.7 – 11.4 mmol/L | > 1000 mg/dL > 11.4 mmol/L life-threatening consequences |
| Uric acid, serum-high (hyperuricemia) | > ULN – 10 mg/dL ≤ 0.59 mmol/L without physiologic consequences | N/A | > ULN – 10 mg/dL ≤ 0.59 mmol/L with physiologic consequences | > 10 mg/dL > 0.59 mmol/L life-threatening consequences |

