Bilirubin (hyperbilirubinemia)	> ULN – $1.5 \times ULN$	> $1.5 - 3.0 \times ULN$	> $3.0 - 10.0 \times ULN$	> $10.0 \times ULN$
Calcium, serum-low (hypocalcemia)	< LLN – 8.0 mg/dL < LLN – 2.0 mmol/L	< 8.0 – 7.0 mg/dL < 2.0 – 1.75 mmol/L	< 7.0 – 6.0 mg/dL < 1.75 – 1.5 mmol/L	< 6.0 mg/dL < 1.5 mmol/L
Calcium, serum-high (hypercalcemia)	> ULN – 11.5 mg/dL > ULN – 2.9 mmol/L	> 11.5 – 12.5 mg/dL > 2.9 – 3.1 mmol/L	> 12.5 – 13.5 mg/dL > 3.1 – 3.4 mmol/L	> 13.5 mg/dL > 3.4 mmol/L
Cholesterol, serum-high (hypercholesterolemia)	> ULN – 300 mg/dL > ULN – 7.75 mmol/L	> 300 – 400 mg/dL > 7.75 – 10.34 mmol/L	> 400 – 500 mg/dL > 10.34 – 12.92 mmol/L	> 500 mg/dL > 12.92 mmol/L
Creatinine	> ULN – $1.5 \times ULN$	> $1.5 - 3.0 \times ULN$	> $3.0 - 6.0 \times ULN$	> $6.0 \times ULN$
GGT (γ -Glutamyl transpeptidase)	> ULN – $3.0 \times ULN$	> $3.0 - 5.0 \times ULN$	> $5.0 - 20.0 \times ULN$	> $20.0 \times ULN$
Glucose, serum-high (hyperglycemia)	Fasting glucose value: > ULN – 160 mg/dL > ULN – 8.9 mmol/L	Fasting glucose value: > 160 – 250 mg/dL > 8.9 – 13.9 mmol/L	> 250 – 500 mg/dL; > 13.9 – 27.8 mmol/L; hospitalization indicated	> 500 mg/dL; > 27.8 mmol/L; life-threatening consequences

Sponsor's Grading for Laboratory Values				
	Grade 1	Grade 2	Grade 3	Grade 4
Glucose, serum-low (hypoglycemia)	< LLN – 55 mg/dL < LLN – 3.0 mmol/L	< 55 – 40 mg/dL < 3.0 – 2.2 mmol/L	< 40 – 30 mg/dL < 2.2 – 1.7 mmol/L	< 30 mg/dL < 1.7 mmol/L life-threatening consequences
Phosphate, serum-low (hypophosphatemia)	<LLN- 2.5 mg/dL <LLN – 0.8 mmol/L	<2.5-2.0 mg/dL <0.8-0.6 mmol/L	<2.0-1.0 mg/dL <0.6-0.3 mmol/L	< 1.0 mg/dL < 0.3 mmol/L life-threatening consequences
Potassium, serum-high (hyperkalemia)	> ULN – 5.5 mmol/L	> 5.5 – 6.0 mmol/L	> 6.0 – 7.0 mmol/L; hospitalization indicated	> 7.0 mmol/L life-threatening consequences
Potassium, serum-low (hypokalemia)	< LLN – 3.0 mmol/L	< LLN – 3.0 mmol/L; symptomatic intervention indicated	< 3.0 – 2.5 mmol/L; hospitalization indicated	< 2.5 mmol/L life-threatening consequences
Sodium, serum-high (hypernatremia)	> ULN – 150 mmol/L	> 150 – 155 mmol/L	> 155 – 160 mmol/L; hospitalization indicated	> 160 mmol/L; life-threatening consequences
Sodium, serum-low (hyponatremia)	< LLN – 130 mmol/L	NA	< 130 – 120 mmol/L	< 120 mmol/L; life-threatening consequences

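### Grade 2 high glucose is defined on a fasting value but counted at visits with no fasting requirement; triglycerides share only a fasting-state mismatch with baseline

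*SAP*

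**What the plan says.** - **Scope of the count.** SAP 5.6.3: "The incidence of TEMAVs will be summarized over all scheduled and unscheduled visits for the parameters with defined notable ranges given in Section 13.1". For every parameter except phosphate, "a value will be determined to be a TEMAV if the post baseline NCI grade increases from baseline and the post baseline grade is greater"; the threshold is Grade 2 or higher. No restriction by fasting status is given.
- **Glucose grades.** In SAP 13.1, as in protocol Appendix 1, Grade 2 high glucose reads "Fasting glucose value: > 160 – 250 mg/dL > 8.9 – 13.9 mmol/L". Grade 1 has the same fasting label. Grade 3 reads "> 250 – 500 mg/dL; > 13.9 – 27.8 mmol/L; hospitalization indicated", with no fasting label, and Grade 4 has none either. Low glucose has none at any grade.
- **Triglyceride grades.** Protocol Appendix 1, which SAP 13.1 names as its source, sets Grade 1 at 150 to 300 mg/dL and Grade 2 above 300 to 500 mg/dL. No grade mentions fasting.
- **When fasting is required.** Protocol Table 2, footnote a, for glucose and the lipid panel: "Fasting samples to be taken at Baseline and at Visit 7 (end of Maintenance Period) or Early Discontinuation". Protocol Table 5, footnote n: "Fasting samples to be taken at indicated time points for glucose and lipid panel". That footnote is attached to the laboratory draws at Visit 2, Visit 7 and Early Discontinuation. It is absent at Visit 1, Visit 4, Follow-up and Unscheduled.
- **Other summaries.** SAP 5.6.3 also plans change from baseline by visit and at end of treatment, shift tables by visit and at end of treatment, and shift tables to the highest and lowest value on treatment.

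**The concern.** Grade 2 is the entry point to the TEMAV table. For high glucose it is defined for a fasting sample, yet the counting rule applies it to every post-baseline draw, including draws where the protocol asks for no fasting. A sample taken after a meal can exceed 160 mg/dL without any drug effect and enter the table as treatment-emergent.

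The protocol's revision history records that fasting at baseline and end of treatment was introduced after a regulator raised weight gain and triglycerides. Pooling those draws with draws of unspecified fasting state gives up part of that control in the tables meant to show a metabolic signal. At stake is how readable one descriptive safety table is; no efficacy result is affected.

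**Working it through.** The plan states no figure on this point, so there is none to reproduce. As a side check, 160, 250 and 500 mg/dL divided by 18.016 give 8.88, 13.88 and 27.75 mmol/L. These match the table's 8.9, 13.9 and 27.8, so the cut-offs themselves are consistent.

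**Step 1. Which draws are graded, and which are fasting-designated** (protocol Tables 2, 5 and 6; SAP 5.6.3, 8.2.1 and 8.2.2)

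| Draw | Fasting required | Role in the TEMAV count |
|---|---|---|
| Visit 2 | yes | normally the baseline (last non-missing pre-dose value) |
| Visit 4 | no | counted |
| Visit 7 | yes | counted |
| Early Discontinuation | yes | counted |
| Unscheduled | no | counted |
| 4-week Follow-up | no | normally outside, since the laboratory window ends 14 days after last dose |

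Of the two scheduled on-treatment draws for a completer (Visits 4 and 7), one has no fasting requirement.

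**Step 2. Which summaries mix fasting states.** The pooled TEMAV count and the highest-value shift table mix them. The Week 4 change summary compares a fasting-designated baseline with a value of unspecified state. SAP 8.2.2 maps early-withdrawal visits to weeks, and its laboratory table assigns Days 2 to 76 to Week 4. An Early Discontinuation draw in that range therefore sits in the same column as Visit 4, so analysis week cannot identify the fasting-designated draws; actual visit can.

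**Step 3. Size, as an illustration.** The documents give neither the true TEMAV rates nor the chance that a non-fasting draw alone produces a Grade 2 value. Assumptions: true rates 2% (placebo) and 8% (perampanel); a false-positive chance f that is equal in both arms and independent of true status; 71 per arm as planned.

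- Observed rate = 1 − (1 − p)(1 − f)
- Difference = (1 − f)(0.08 − 0.02)
- Added subjects per arm = 71(1 − p)f
- Standard error (SE) of the difference = √{[a(1 − a) + b(1 − b)]/71}, where a and b are the observed rates

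At f = 10%: placebo 1 − 0.98 × 0.90 = 11.8%; perampanel 1 − 0.92 × 0.90 = 17.2%; difference 0.90 × 6.0 = 5.4 points; added subjects 71 × 0.98 × 0.10 = 7.0 and 71 × 0.92 × 0.10 = 6.5.

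| f | Placebo | Perampanel | Difference (points) | Added subjects (placebo, perampanel) | SE (points) | Odds ratio |
|---|---|---|---|---|---|---|
| 0 | 2.0% | 8.0% | 6.0 | 0, 0 | 3.6 | 4.26 |
| 3% | 4.9% | 10.8% | 5.8 | 2.1, 2.0 | 4.5 | 2.32 |
| 10% | 11.8% | 17.2% | 5.4 | 7.0, 6.5 | 5.9 | 1.55 |
| 20% | 21.6% | 26.4% | 4.8 | 13.9, 13.1 | 7.2 | 1.30 |

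The difference shrinks only by the factor (1 − f), while incidence and standard error rise. With equal true rates (5% in each arm) the observed difference is 0 at every f.

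**The case against.** The strongest case on the other side has five parts.

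1. *The key facts are open.* The protocol does not say that Visit 4 samples are taken after food; it only does not ask for fasting. The fasting label could also mean that a non-fasting value is not gradable at Grades 1 and 2. SAP section 9 leaves derivation rules to separate specifications. This stands as a limit on wording. It does not remove the problem, because the rule as written takes all visits and says nothing about such samples.
2. *Triglycerides.* A reader might infer that their cut-offs are meant for fasting samples too, because the lipid panel is to be drawn fasting at the marked visits. The grades do not say so. For this parameter only the baseline-to-Visit 4 mismatch stands.
3. *A like-for-like comparison is already planned.* The Visit 7 and end-of-treatment summaries compare mainly fasting-designated draws with a fasting-designated baseline. SAP 5.6.3 also counts subjects with two consecutive abnormal records. This stands, so it would be wrong to say that the plan can neither confirm nor exclude a metabolic signal.
4. *Scale.* The fall in the odds ratio looks dramatic, but SAP 5.6.3 plans only numbers and percentages by arm. On that scale the loss is small. This stands, although the added noise in the table is real.
5. *An over-wide remedy would do harm.* Restricting all glucose TEMAVs to fasting draws would drop low-glucose and Grade 3-4 high-glucose values at Visit 4 and unscheduled visits. Those grades have no fasting label, and a safety concern may have prompted the draw. This stands and shapes the fix.

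**Conclusion.** The point holds in a limited form. For Grade 2 high glucose, a cut-off defined on a fasting value is applied to Visit 4 and unscheduled draws for which the protocol requires no fasting, and the SAP gives no rule for them. For triglycerides, a fasting-designated baseline is compared with a Visit 4 value of unspecified state in the pooled TEMAV count, the highest-value shift table and the Week 4 change summary.

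A reader might go further and infer that post-meal values will appear as abnormalities caused by perampanel. The documents do not support that. Both arms have the same draws, so a shared false-positive rate raises both columns and leaves a zero difference at zero.

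Under the assumed 2% and 8%, false-positive rates of 3% to 20% add about 2 to 14 subjects per arm of 71 and reduce a 6.0-point difference to between 5.8 and 4.8 points. These rates are illustrative, and the equal, independent f is itself an assumption. The change is worth making because it is cheap and makes the metabolic safety table interpretable; the primary analysis does not depend on it.

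**What to change.** Amend SAP 5.6.3 as follows:

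- Base Grade 2 high-glucose TEMAVs on the fasting-designated draws (Visit 2 as baseline; Visit 7 or Early Discontinuation after it), selected by actual visit and not by analysis week, or on samples with recorded fasting status.
- Tabulate Grade 2 high-glucose values from other draws in a separate row marked *fasting not required*.
- Show triglyceride TEMAVs and highest-value shifts twice: for fasting-designated draws and for all draws.
- Keep low-glucose TEMAVs and Grade 3-4 high-glucose TEMAVs counted over all scheduled and unscheduled visits.

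All other parameters stay as planned. The cost is a short SAP addition, a selection by visit in programming and one or two extra table rows. The drawback is that the fasting-based Grade 2 glucose count rests on fewer draws; the separate row keeps the remaining values in view.
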